11.1 Analysis of the Primary Outcome

To address the aim for the primary analysis (**Aim 1**), longitudinal scores from baseline through Month 12 will be analyzed using a mixed effects model for repeated measures (MMRM) to test differences in ADAS-Cog-Exec (composite) change scores between intervention groups in the mITT Population, with type I error level set at 0.05.

The MMRM model includes terms for time, intervention assignment, and baseline ADAS-Cog-Exec plus covariates that include site, ApoE4 carrier status, sex, and additional covariates meeting the criteria below. The primary test compares group changes from baseline to the mean score obtained across the Month 6 and Month 12 assessments. When Month 6 or Month 12 data are missing for a participant, the endpoint consists of the score obtained at the available assessment visit.

When an individual test score of the ADAS-Cog-Exec composite is missing or not administered and the examiner indicated it is missing “for cognitive reasons”, the worst possible score is assigned for that individual test prior to constructing the ADAS-Cog-Exec score.

Potential confounders (baseline Walk Test time, age, education, 3MSE baseline score, and use of cholinesterase inhibitors) will be included in efficacy analyses as covariates if the following two conditions are satisfied: (1) imbalance at baseline ($p < 0.1$) and, (2) association between the covariate and the response ($p < 0.15$). Safety data will be analyzed using exact contingency table methods by intervention group assignment.

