### 5.4 Efficacy Analysis

#### 5.4.1 Analysis of Primary Outcome

To address **Aim 1** for the primary efficacy analysis, longitudinal scores from baseline through the first 12 months will be analyzed using a mixed effects model for repeated measures (MMRM) to assess differences in scores between intervention groups. The MMRM model will include terms for time, intervention, and baseline ADAS-Cog-Exec, intervention-by-time

interaction, baseline ADAS-Cog-Exec by time interaction, plus covariates that include site, ApoE4 carrier status, sex, and additional covariates meeting the criteria below.

Time will be treated as categorical. An analysis of covariance model imputing missing data with multiple imputation will be used as a sensitivity analysis. As a second sensitivity analysis, a similar MMRM model will be fit with time modeled as a continuous factor. If the longitudinal patterns over time are markedly non-linear, such as might occur due to learning effects, a quadratic term for time will be included in the model. In this case the intervention-by-time linear term assesses whether there is a relative difference between intervention groups that grows linearly with time. Potential confounders (baseline Walk Test time, age, education, 3MSE baseline score, and use of cholinesterase inhibitors) will be included in efficacy analyses as covariates if the following two conditions are satisfied: (1) imbalance at baseline ( $p < 0.1$ ) and, (2) association between the covariate and the response ( $p < 0.15$ ). Safety data will be analyzed using exact contingency table methods by intervention group assignment.

Differences in the primary outcome of change in ADAS-Cog-Exec between intervention groups will be tested at the two-sided 5% significance level. No adjustment to the type 1 error level will be made for secondary analyses.

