11.2 Analyses of Key Secondary Outcomes

11.2.1 A key second outcome is the intervention-related change in the ADAS-Cog-Exec for the mITT Pre-Pandemic Subset, which will be examined using the same analytic approach described for Aim 1.

11.2.2 Other secondary outcomes to be examined in the mITT Population, using a similar analytic approach as described for Aim 1, include:

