14.2 ASL MRI

ASL MRI of the brain is performed to quantify cerebral blood flow (CBF). The intervention effect will be assessed by examining group differences in mean change in CBF values from baseline to Month 12. The key ASL MRI outcomes include hippocampal CBF, and perfusion in the prefrontal and AD signature meta-ROI composites that were described for the volumetric MRI analyses. Composites for these analyses, described again below, reflect mean CBF values across left and right brain hemispheres.

- **AD Signature Composite:** parahippocampus, fusiform, inferior temporal, middle temporal, inferior-parietal
- **Prefrontal Composite:** superior frontal, caudal-middle frontal, rostral-middle frontal, pars opercularis, pars triangularis

Exploratory outcomes include whole brain, gray matter, and white matter perfusion, and voxel-wise analysis of intervention-related changes in CBF.

Change in CBF appears to be an early and sensitive indicator of neurodegeneration associated with AD and may provide an early index of the intervention's ability to alter AD-related atrophy and brain function. CBF changes in prefrontal regions have also been reported in smaller studies of aerobic exercise in adults with MCI.

All ASL MRI will undergo quality control (QC) for image artifacts, tagging error, excessive motion, registration between ASL and volumetric MRIs, and other factors. Images passing QC checks will be processed through an in-house program that [name] developed, which includes quantification of CBF into a physiological unit (ml/100g tissue/min), co-registration with T1w structural images, and partial volume correction. The baseline and follow-up CBF images will be normalized into a standard image template (i.e., MNI template) using SPM. The CBF values in prefrontal and AD signature composite regions, hippocampus, and whole brain gray and white matter will be computed and returned to the statistical team for analysis. The exploratory voxel-wise linear regression that contrasts intervention effects will be performed after site variations are harmonized and covariates (identified above for primary analysis) are adjusted. A minimum cluster size will be specified to control false positives.

The number of images that are not quantifiable due to scan alignment failure will be summarized by study arm.

15 Evaluation of Safety Measures

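### The primary model adjusts for five baseline covariates only if they happen to be imbalanced, so it usually forgoes precision that a fixed list would secure

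*SAP*

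**What the plan says.** SAP 11.1 puts time, intervention and baseline ADAS-Cog-Exec in the MMRM, "plus covariates that include site, ApoE4 carrier status, sex, and additional covariates meeting the criteria below". Site, ApoE4 and sex are the randomisation strata (SAP section 3), so the baseline score and every stratification factor are always in the model.

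The additional covariates come from a named list of five. Protocol 5.4.1 introduces it as "Potential confounders (baseline Walk Test time, age, education, 3MSE baseline score, and use of cholinesterase inhibitors", and SAP 11.1 has the same list. Each of the five "will be included in efficacy analyses as covariates if the following two conditions are satisfied": imbalance between arms at baseline with p<0.1, and "association between the covariate and the response" with p<0.15. Both must hold. Candidates and thresholds are identical in the two documents.

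The approach is reused. The key secondary outcome is the change in ADAS-Cog-Exec in the Pre-Pandemic Subset, "which will be examined using the same analytic approach described for Aim 1". The other secondary and exploratory analyses also refer back to Aim 1 (SAP 11.2 and 11.3; Protocol 5.4.2).

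**The concern.** In a randomised trial the main reason to adjust for a baseline covariate is that it predicts the outcome, because adjustment then shrinks the standard error of the treatment effect. Under this rule prediction is not enough: the covariate must also differ between arms at p<0.1. None of the five is a stratification factor, so any difference between arms arises by chance, and a test at p<0.1 finds one about one time in ten whether the covariate predicts the outcome strongly or not at all. Most strongly prognostic candidates would be left out, and the covariates in the primary model would be known only after the imbalance and association tests had been run. What is at stake is precision and a primary model fixed in advance.

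**Working it through.** **Inputs.** From the documents: difference 1.5, SD 4.1, two-sided alpha 5%, power 80%, attrition 20%, required N 291, enrolled 296 (SAP section 4); thresholds 0.1 and 0.15 (SAP 11.1); Wilcoxon and Fisher tests for baseline comparisons (SAP section 10). Assumed, because the documents do not say: the extra R2 of the five covariates beyond the fixed terms (0 to 0.20; up to 0.30 with a single covariate), 14 sites, 20% cholinesterase-inhibitor use, and a correlation of -0.5 between 3MSE and the baseline composite.

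**1. The plan's own figure.** Per arm, n = 2 × [4.1 × (1.960 + 0.842) / 1.5]² = 117.3, rounded up to 118, or 236 in total. Allowing for attrition, 236 / 0.8 = 295 (293.2 without rounding), within 2% of the stated 291. This calculation does not involve the covariate rule. The analysed number used below is 296 × 0.8 = 236.8, taken as 236.

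**2. How often a candidate enters.** With one normally distributed candidate, 118 per arm and 10,000 trials per setting, the Wilcoxon test gave p<0.1 in 9.4 to 10.2% of trials at every R2. The association condition passed in about 76% of trials at R2 0.02, 98% at 0.05 and essentially all at 0.10 or more. The candidate was dropped in 92% of trials at R2 0.02 and in 90 to 91% at 0.05 or more. For the binary candidate, exact enumeration of Fisher's test gives a pass rate of 6 to 8% at 10 to 40% use. If the five were independent, at least one would pass the imbalance condition in 1 - 0.9⁵ = 41% of trials.

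**3. Power with all five candidates.** 8,000 trials per setting, effect 1.5/4.1 = 0.366 of the SD left after the fixed terms, extra R2 spread equally over the five. Every model contains treatment, baseline score, site, ApoE4 and sex. Differences are taken before rounding.

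| Extra R2 | No extra covariates | Rule | All five fixed | Fixed minus rule (points) |
|---|---|---|---|---|
| 0 | 0.778 | 0.775 | 0.769 | -0.6 |
| 0.02 | 0.766 | 0.764 | 0.763 | -0.2 |
| 0.05 | 0.764 | 0.765 | 0.779 | +1.4 |
| 0.10 | 0.763 | 0.767 | 0.798 | +3.1 |
| 0.20 | 0.774 | 0.785 | 0.855 | +6.9 |

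The Monte Carlo error of the paired difference is 0.2 to 0.4 points. If 266 are analysed (10% assumed to have neither visit), the differences are -0.6, +0.5, +1.5, +2.8 and +5.7. If one covariate carries all the extra R2 (236 analysed), they are +1.1, +2.9 and +7.1 at 0.05, 0.10 and 0.20. The simpler simulation of step 2 gives 0.8158 - 0.7984 = +1.7, 0.8335 - 0.8032 = +3.0 and 0.8808 - 0.8146 = +6.6 points at the same values.

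**4. Type I error under the rule.** 0.050, 0.054, 0.042 and 0.039 at extra R2 0, 0.05, 0.10 and 0.20 (Monte Carlo error about 0.0024). The simpler simulation gives 0.050, 0.047, 0.044 and 0.040 at 0.05, 0.10, 0.20 and 0.30.

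**5. If the fixed terms already reduce the SD.** Step 3 treats 4.1 as the SD remaining after the fixed terms, whereas the SAP uses it as the SD of 12-month ADAS-Cog change. Let the fixed terms explain a share f of that variance. The noncentrality is then (1.5/4.1) × √(236/4) / √[(1 - f)(1 - R2)]. Taking R2 from 0 to 0.10, power from the noncentral t (234 degrees of freedom) rises from 79.9% to 83.9% at f = 0 (+4.0), from 87.9% to 91.0% at f = 0.20 (+3.1) and from 91.7% to 94.1% at f = 0.30 (+2.4). This compares fixed adjustment with none and ignores covariate imbalance, so it shows how the gain shrinks; it does not replace step 3.

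**The case against.** The best defence is that the rule does what its label promises. Both documents call the five potential confounders, so the aim is to deal with chance imbalance, and leaving out a balanced prognostic variable does not bias a randomised comparison. The rule is pre-specified, and the planned power rests on an unadjusted t-test, so no stated power figure is missed. Gains of about 3 points or more need an extra R2 of about 0.10 beyond baseline composite, site, ApoE4 and sex. No document supports that value, and 3MSE, as a global cognitive measure, probably overlaps with the baseline composite. All of this stands. It limits the point to precision and makes the gain conditional. It does not show that the rule is as good as a fixed list, which costs under one point if the five add nothing.

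A reader might infer more than the documents support:

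- **Inflated false positives or bias.** Step 4 shows a nominal to mildly conservative test.
- **An unworkable rule, because the association test is unnamed and the response loosely described.** SAP 11.1 says "longitudinal scores from baseline through Month 12 will be analyzed" and also speaks of a model to "test differences in ADAS-Cog-Exec (composite) change scores between intervention groups". The detail is missing, but the same section states the primary contrast. Switching between unadjusted and adjusted association tests moved the rule's power by less than 0.4 points.
- **Conflicting instructions on carrying covariates over.** SAP 14.2 says "covariates (identified above for primary analysis) are adjusted", but of a single exploratory voxel-wise regression. It does not settle, or contradict, what is done in other populations.
- **Cholinesterase-inhibitor use after randomisation entering the model.** The first condition concerns imbalance at baseline, which implies baseline use.

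**Conclusion.** The point holds as a cheap improvement. The imbalance condition excludes each candidate in about 90% of trials regardless of its prognostic value, so the primary model depends on chance imbalance and usually forgoes available precision. With 236 analysed, fixing all five changes power by about -1 to +2 points at extra R2 of 0 to 0.05, about +3 at 0.10 and +6 to +7 at 0.20.

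These figures rest on an R2 that the documents do not give, on the assumed inputs listed above, and on carrying the standardised effect of 0.366 from ADAS-Cog over to the composite. Treating 4.1 as the residual SD puts the gains towards the high end. The 90% assumes randomised groups; selection into the mITT population could shift it. Nothing here shows bias, false positives or an underpowered trial.

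**What to change.** Before unblinding, replace the two p-value conditions in SAP 11.1 with fixed inclusion of all five covariates as measured before randomisation, stating that cholinesterase-inhibitor use means use at baseline. Use the same list in every analysis that reuses the primary model. Keep the two-condition model as a sensitivity analysis, and record the departure from Protocol 5.4.1 in the SAP.

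The documents do not show whether the blind is still in place. If it has been broken, keep the stated rule as primary and report the fixed-list model as a labelled sensitivity analysis.

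The cost is a text change, up to five degrees of freedom (about 1 power point or less if none of the five is prognostic) and simple imputation of any missing baseline covariate. No new data are needed, since all five can be taken from screening or baseline procedures.

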11.2 Analyses of Key Secondary Outcomes

11.2.1 A key second outcome is the intervention-related change in the ADAS-Cog-Exec for the mITT Pre-Pandemic Subset, which will be examined using the same analytic approach described for Aim 1.

11.2.2 Other secondary outcomes to be examined in the mITT Population, using a similar analytic approach as described for Aim 1, include:

11.2.2.1 Executive Function and Episodic Memory Composites (details in **Section 13**)

11.2.2.2 MRI measures of regional atrophy and blood flow in the hippocampus, and in prefrontal (superior frontal, caudal-middle frontal, rostral-middle frontal, pars opercularis, pars triangularis) and AD signature (parahippocampus, fusiform, inferior temporal, middle temporal, inferior-parietal) meta-ROI composites (details in **Section 14**)

11.2.2.3 AD biomarkers in CSF (ab42/ab40, ab42/tau, ab42/p-tau) and blood (ab42/ab40)

No adjustment to type 1 error level ($\alpha = 0.05$) will be made for secondary analyses.

11.3 Exploratory Analyses

Exploratory analyses will be conducted using the same approach described for Aim 1.

11.3.1 Test intervention effects in the mITT Pre-Pandemic Subset on the following outcomes:

- 12.2** Intervention effects on a supplemented ADAS-Cog-Exec that includes Letter Fluency (mean of F and L Fluency) will be examined in the mITT Population, the Pre-Pandemic Subset, and the Pandemic Subset using a similar approach described for Aim 1.
- 12.3** Intervention effects on the primary and key secondary outcomes will be examined in the Pandemic Subset using the approach described for Aim 1.
- 12.4** Subgroup analyses testing whether the following variables predict cognitive, vMRI, ASL MRI, and specimen biomarker response to the intervention in the mITT

Population and Pre-Pandemic Subset: sex, age, APOE genotype, baseline biomarker status (CSF: ab42/ab40, ab42/tau, ab42/p-tau; and blood: ab42/ab40).

12.5 In the Pandemic Subset, test whether pandemic-time-in-study altered intervention response on primary and key secondary outcomes. Pandemic-time-in-study coding is provided below.

- **Code 1:** At the time of study pause, participant had completed the Month 6 outcomes assessment (but not the Month 12 outcomes assessment)
- **Code 2:** At the time of study pause, participant was due for Month 6 or Month 12 outcomes assessment but did not complete until after the pause following a brief (6-8 weeks) ramp-up to prescribed intervention intensity.
- **Code 3:** At the time of study pause, participant had not yet completed an outcomes assessment.

13 Analyses of Executive Function and Episodic Memory Composites

Individual test scores included in each composite are listed below. Test scores are converted to z-scores and then averaged to create the composite score. Z-scores for longitudinal change are calculated by subtracting each participant's baseline score from the follow-up score (Month 6, Month 12) to obtain a change score, then dividing each change score by the baseline standard deviation for that measure. Composite scores are computed when 50% or more of the component test scores are available.

13.1 Executive Function Composite

- 1) Trails B: time (adjusted so higher values reflect better performance)
- 2) Digit Symbol Substitution Test (DSST): total correct
- 3) Category Fluency: mean of Animal and Vegetable Fluency
- 4) Letter Fluency: mean of F and L Fluency
- 5) ADAS-Cog 13 Number Cancellation: scaled score (range: 0-5; adjusted so higher values reflect better performance)
- 6) NIH Toolbox Flanker: total corrected score (Toolbox variable= "CSCORE"; variable takes accuracy and RT into consideration and higher scores reflect better performance)
- 7) NIH Toolbox Dimensional Change Card Sort (DCCS): total corrected score (toolbox variable= "CSCORE"; variable takes accuracy and RT into consideration and higher scores reflect better performance)
- 8) CogState One Back (ONB): arcsine square root proportion correct (CogState transformed variable= "ONB ACC")

13.2 Episodic Memory Composite

- 1) Immediate Word Recall (from ADAS-Cog-Exec): mean raw score of 3 trials (adjusted so higher values reflect better performance)
- 2) Delayed Word Recall (from ADAS-Cog-Exec): total raw score (adjusted so higher values reflect better performance)
- 3) CogState Face-Name Associative Memory Exam (FNAME): mean of Face Naming Learning Test Accuracy (CogState variable= "FNLT ACC") and Face Naming Matching Test accuracy (CogState variable= "FNMT ACC") (i.e., (FNLT ACC + FNMT ACC) / 2)

- 4) CogState Behavioral Pattern Separation of Objects (BPSO): probability of naming Distractor/Lure stimulus “Similar” minus the probability of naming a new stimulus “Similar” (CogState pattern separation variable= “BPXT METRIC”; higher scores reflect better performance)
- 5) CogState One Card Learning (OCL): arcsine square root proportion correct (CogState transformed variable= “OCL ACC”)

14 Imaging Analyses

14.1 Volumetric MRI

The intervention effect will be assessed by examining group differences from baseline to Month 12 in mean volumetric MRI change values in three key regions: hippocampus, AD signature composite,³ and prefrontal composite. Regions included in each meta-ROI composite are listed below (Desikan brain atlas). Composite values will reflect mean volumes across left and right brain hemispheres.

- **AD Signature Composite**

1. parahippocampus
2. fusiform
3. inferior temporal
4. middle temporal
5. inferior-parietal

- **Prefrontal Composite**

1. superior frontal
2. caudal-middle frontal
3. rostral-middle frontal
4. pars opercularis
5. pars triangularis

Additional exploratory vMRI measures to be examined include whole brain, ventricular and entorhinal volumes.

Hippocampal volume derived from MRI correlates with histological hippocampal volume and degree of neuronal loss and AD pathology appear to be an early and sensitive indicator of neurodegeneration associated with AD. Exercise effects on cortical thickness have previously been reported in prefrontal brain regions, particularly in dorsolateral areas.⁴⁻⁶ Longitudinal MRI measures of regional and whole brain volumetric change provide a valuable complement to cognitive measures in that they are not influenced by temporary symptomatic improvements, and they may provide an early index of the intervention’s ability to influence AD-related atrophy.

The analysis of structural change will be performed through Quarc nonlinear registration⁷ comparing each participant’s follow-up scan to the initial baseline scan. The Month 12 scan will be registered to the baseline scan. The procedure provides percent deformation within regions of interest (ROIs) obtained through segmentation of the baseline scan. The registration of serially acquired brain volumes yields a deformation field that represents the volumetric shift of internal structure required for optimal overlaying of the two scans. The anatomically based segmentation is overlaid on the smoothed voxel-wise deformation field and an average percent

deformation is created for each ROI. Visual QC of registration is performed and values from scans passing QC are returned to the statistical team for analysis.

The number of images that are not quantifiable due to scan alignment failure will be summarized by study arm.

14.2 ASL MRI

ASL MRI of the brain is performed to quantify cerebral blood flow (CBF). The intervention effect will be assessed by examining group differences in mean change in CBF values from baseline to Month 12. The key ASL MRI outcomes include hippocampal CBF, and perfusion in the prefrontal and AD signature meta-ROI composites that were described for the volumetric MRI analyses. Composites for these analyses, described again below, reflect mean CBF values across left and right brain hemispheres.

- **AD Signature Composite:** parahippocampus, fusiform, inferior temporal, middle temporal, inferior-parietal
- **Prefrontal Composite:** superior frontal, caudal-middle frontal, rostral-middle frontal, pars opercularis, pars triangularis

Exploratory outcomes include whole brain, gray matter, and white matter perfusion, and voxel-wise analysis of intervention-related changes in CBF.

Change in CBF appears to be an early and sensitive indicator of neurodegeneration associated with AD and may provide an early index of the intervention's ability to alter AD-related atrophy and brain function. CBF changes in prefrontal regions have also been reported in smaller studies of aerobic exercise in adults with MCI.

All ASL MRI will undergo quality control (QC) for image artifacts, tagging error, excessive motion, registration between ASL and volumetric MRIs, and other factors. Images passing QC checks will be processed through an in-house program that [name] developed, which includes quantification of CBF into a physiological unit (ml/100g tissue/min), co-registration with T1w structural images, and partial volume correction. The baseline and follow-up CBF images will be normalized into a standard image template (i.e., MNI template) using SPM. The CBF values in prefrontal and AD signature composite regions, hippocampus, and whole brain gray and white matter will be computed and returned to the statistical team for analysis. The exploratory voxel-wise linear regression that contrasts intervention effects will be performed after site variations are harmonized and covariates (identified above for primary analysis) are adjusted. A minimum cluster size will be specified to control false positives.

The number of images that are not quantifiable due to scan alignment failure will be summarized by study arm.

15 Evaluation of Safety Measures

